12.2.1 Definitions

12.2.1.1 Evaluable for objective response: Patients who exhibit objective disease progression prior to the end of cycle 1 will be considered evaluable for response. For all other patients, only those patients who have measurable disease present at baseline, have received at least one cycle of therapy, and have had their disease re-evaluated will be considered evaluable for response.

12.2.1.2 Evaluable Non-Target Disease Response: Patients who have lesions present at baseline that are evaluable but do not meet the definitions of measurable disease, have received at least one cycle of therapy, and have had their disease re-evaluated will be considered evaluable for non-target disease. The response assessment is based on the presence, absence, or unequivocal progression of the lesions.

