12.2.2 Disease Parameters

12.2.2.1 Measurable disease: Measurable lesions are defined as those that can be accurately measured in at least one dimension (longest diameter to be recorded) as ≥ 20 mm by chest x-ray, as ≥ 10 mm with CT scan, or ≥ 10 mm with calipers by clinical exam. All tumor measurements must be recorded in millimeters (or decimal fractions of centimeters).

Note: Tumor lesions that are situated in a previously irradiated area must show definitive evidence of progression to be considered evaluable.

12.2.2.2 Malignant lymph nodes: To be considered pathologically enlarged and measurable, a lymph node must be ≥ 15 mm in short axis when assessed by CT scan (CT scan slice thickness no greater than 5 mm). At baseline and in follow-up, only the short axis will be measured and followed.

12.2.2.3 Non-measurable disease: All other lesions (or sites of disease), including small lesions (longest diameter < 10 mm or pathological lymph nodes with ≥ 10 to < 15 mm short axis), are considered non-measurable disease. Bone lesions, leptomeningeal disease, ascites, pleural/pericardial effusions, lymphangitis cutis/pulmonitis, inflammatory breast disease, and abdominal masses (not followed by CT or MRI), are considered as non-measurable.

Note: Cystic lesions that meet the criteria for radiographically defined simple cysts should not be considered as malignant lesions (neither measurable nor non-measurable) since they are, by definition, simple cysts. 'Cystic lesions' thought to represent cystic metastases can be considered as measurable lesions, if they meet the definition of measurability described above. However, if non-cystic lesions are present in the same patient, these are preferred for selection as target lesions.

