12.3 Response Criteria for Patients with Solid Tumors and Evaluable Disease

12.3.1 Evaluable Disease

The presence of at least one lesion, with no lesion that can be accurately measured in at least one dimension. Such lesions may be evaluable by nuclear medicine techniques, immunocytochemistry techniques, tumor markers or other reliable measures.

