12.3.3 Partial response

Partial responses cannot be determined in patients with evaluable disease

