12.4 Response Criteria for Neuroblastoma Patients with MIBG Positive Lesions

12.4.1 MIBG Positive Lesions

Patients who have a positive MIBG scan at the start of therapy will be evaluable for MIBG response. The use of ¹²³I for MIBG imaging is recommended for all scans. If the patient has only one MIBG positive lesion and that lesion was radiated, a biopsy must be done at least 28 days after radiation was completed and must show viable neuroblastoma.

12.4.2 The following criteria will be used to report MIBG response by the treating institution:

Complete response: Complete resolution of all MIBG positive lesions

Partial Response: Resolution of at least one MIBG positive lesion, with persistence of other MIBG positive lesions

Stable disease: No change in MIBG scan in number of positive lesions

Progressive disease: Development of new MIBG positive lesions

12.4.3 The response of MIBG lesions will be assessed on central review using the Curie

[figure not shown]
scale14 as outlined below. Central review responses will be used to assess efficacy for study endpoint. See [Section 8.2](#) for details on transferring images to the Imaging Research Center.

NOTE: This scoring should also be done by the treating institution for end of course response assessments.

The body is divided into 9 anatomic sectors for osteomedullary lesions, with a 10th general sector allocated for any extra-osseous lesion visible on MIBG scan. In each region, the lesions are scored as follows. The **absolute extension score** is graded as:

- 0 = no site per segment,
- 1 = 1 site per segment,
- 2 = more than one site per segment,
- 3 = massive involvement (>50% of the segment).

The **absolute score** is obtained by adding the score of all the segments. See diagram of sectors below:

The **relative score** is calculated by dividing the absolute score at each time point by the corresponding pre-treatment absolute score. The relative score of each patient is calculated at each response assessment compared to baseline and classified as below:

1. **Complete response:** all areas of uptake on MIBG scan completely resolved. If morphological evidence of tumor cells in bone marrow biopsy or aspiration is present at enrollment, no tumor cells can be detected by routine morphology on two subsequent bilateral bone marrow aspirates and biopsies done at least 21 days apart to be considered a **Complete Response**.

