12.4.4 Overall Response Assessment

Table 5: Overall Response Evaluation for Neuroblastoma Patients and MIBG Positive Disease Only

If patients are enrolled without disease measurable by CT/MRI, any new or newly identified lesion by CT/MRI that occurs during therapy would be considered progressive disease.

MIBG	CT/MRI	Bone Scan	Bone Marrow	Catechol	Overall
PD	Any	Any	Any	Any	PD
Any	New Lesion	Any	Any	Any	PD
Any	Any	PD	Any	Any	PD
Any	Any	Any	PD	Any	PD
SD	No New Lesion	Non-PD	Non-PD	Any	SD
PR	No New Lesion	Non-PD	Non-PD	Any	PR
CR	No New Lesion	Non-PD	Non-PD	Elevated	PR
CR	No New Lesion	CR	CR	Normal	CR

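### MIBG-only neuroblastoma: Section 12.4 allows a PR that Section 12.3.3 rules out, and Section 12.2.1.1 counts these patients for objective response only if they progress in cycle 1

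*Combined protocol and SAP*

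**What the plan says.** Section 4.1.4 admits patients with measurable or evaluable disease and takes both definitions from Sections 12.2 and 12.3. Three sets of rules then reach a neuroblastoma patient whose disease shows on MIBG but not measurably on CT or MRI.

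- **Section 12.2.** Under 12.2.2.1, "Measurable lesions are defined as those that can be accurately measured in at least one dimension", by x-ray, CT or calipers; MIBG uptake is not a listed method, and 12.2.2.3 classes bone lesions as non-measurable. Section 12.2.1.1 opens with an exception: "Patients who exhibit objective disease progression prior to the end of cycle 1 will be considered evaluable for response". For everyone else it counts "only those patients who have measurable disease present at baseline, have received at least one cycle of therapy, and have had their disease re-evaluated". Under 12.2.1.2, patients with evaluable but non-measurable lesions "will be considered evaluable for non-target disease". Table 2 in 12.2.5, for non-measurable disease, has no PR category.
- **Section 12.3.** On evaluable disease, 12.3.1 says: "Such lesions may be evaluable by nuclear medicine techniques, immunocytochemistry techniques, tumor markers or other reliable measures". Section 12.3.2 allows CR. Section 12.3.3 says: "Partial responses cannot be determined in patients with evaluable disease".
- **Section 12.4.** "Patients who have a positive MIBG scan at the start of therapy will be evaluable for MIBG response". Section 12.4.3 gives PR for a relative Curie score up to 0.5 and assigns the central MIBG review to the efficacy endpoint. Section 12.4.4 contains "Table 5: Overall Response Evaluation for Neuroblastoma Patients and MIBG Positive Disease Only", which assigns an overall CR, PR, SD or PD and expressly considers patients enrolled with nothing measurable on CT or MRI.

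Section 11.5 says only that response follows RECIST and is reported descriptively. It names no denominator and no order of precedence.

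**The concern.** There are two separate problems. The first is the category: the same child, with the same fall in Curie score, has a PR under 12.4 and at best stable disease under 12.3. The second is the denominator: 12.2.1.1 is the only definition of evaluable for objective response, and it admits an MIBG-only child who progresses in cycle 1 while leaving out one who responds. That pushes the objective-response rate downward.

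Antitumor activity is the only secondary aim (1.2.1), and in a study of this size one or two patients can change how active the combination looks. The ambiguity can also reach data collection. Section 8.2.1 triggers central review for CR, PR or stable disease of at least 6 cycles, and footnote 5 to the Section 8.1 table asks for a next-cycle evaluation after a first PR or CR. A site that records a Curie PR as stable disease under 12.3 would not trigger the confirmatory evaluation, and would trigger central review only if the patient stayed stable that long.

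**Working it through.** The plan states no response rate, target or response sample size, so there is no figure to reproduce. The check is a comparison of the text, followed by an illustration.

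**One patient under each rule.** Take an MIBG-only child with nothing measurable at baseline, treated for at least one cycle and re-evaluated.

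| Course | 12.4 and Table 5 | 12.3 | Objective-response set (12.2.1.1) |
|---|---|---|---|
| Relative score 0.5 or less, not resolved | PR | SD (no PR possible) | Out |
| Complete resolution, other Table 5 conditions met | CR | CR | Out |
| Stable | SD | SD | Out |
| Progression before end of cycle 1 | PD | PD | In |

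The categories conflict on PR only. The denominator admits only the last row; the others fall to 12.2.1.2.

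**Illustration.** The documents give no count of MIBG-only patients, so every count here is assumed. Let N be the patients treated and followed for response, m the MIBG-only patients among them, b the responders among the other N − m (all taken to have measurable disease), p and c the MIBG PRs and CRs, and e the MIBG-only patients progressing in cycle 1. Sections 12.3 and 12.4 set no overall denominator, so everyone they classify is counted.

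- 12.4: (b + p + c)/N
- 12.2.1.1: b/(N − m + e)
- 12.3: (b + c)/N

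With N = 12 (the scale of the 12 additional patients projected in 11.1.1), m = 2 and b = 1:

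| The two MIBG-only patients | 12.4 | 12.2.1.1 | 12.3 |
|---|---|---|---|
| A: one PR, one stable | 2/12 = 16.7% | 1/10 = 10.0% | 1/12 = 8.3% |
| B: one PR, one CR | 3/12 = 25.0% | 1/10 = 10.0% | 2/12 = 16.7% |
| C: one PR, one progressing in cycle 1 | 2/12 = 16.7% | 1/11 = 9.1% | 1/12 = 8.3% |

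Case C shows the asymmetry: the early progressor is counted and the responder is not.

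**Range.** Keep b = 1 and p = 1, take m as 1, 2 or 4, and, where m allows, add one CR or one early progression:

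- N = 12: 16.7–25.0% under 12.4, 9.1–12.5% under 12.2.1.1, 8.3–16.7% under 12.3.
- N = 36 (the expected overall maximum in 11.1.1): 5.6–8.3%, 2.9–3.1% and 2.8–5.6%.

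The values 12 and 36 are used for scale only; Section 11.1.1 derives them from evaluability for toxicity, not for response.

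**The case against.** The best defence is that the specific section governs the general one. Neuroblastoma is divided by table title: Table 3 in 12.2.5 for measurable disease, Table 5 for MIBG-positive disease only. Section 12.4 has its own evaluability sentence and its own link to the efficacy endpoint. As a reading of intent on the category this is reasonable, and most readers would probably classify by Table 5. It does not settle the matter. No section states that precedence, and 12.2 is not confined to other tumors, since its Table 3 covers neuroblastoma. Section 12.4.5 sends best response to a Section 12.8 that does not exist. Above all, 12.4 sets no objective-response denominator, so 12.2.1.1 still applies even if 12.4 decides the category.

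Several limits do stand:

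- A reader might infer that MIBG-only patients are not evaluable for response at all. Section 12.2.1.2 keeps them evaluable for non-target disease; what they lose is objective response.
- A reader might infer that 12.3 denies them any response. Section 12.3.2 allows CR.
- A reader might put a 12.4 numerator over a 12.2.1.1 denominator, which in case A gives 2/10 = 20.0%. No section prescribes that mixture.
- The asymmetry is not special to MIBG. Any evaluable-only patient, such as one with bone-only disease, meets it.
- Excluding known marrow involvement (4.2.6) probably reduces the number of MIBG-only patients, though it does not remove them.

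**Conclusion.** The inconsistency is in the current text and should be corrected. For MIBG-only patients, 12.4 and 12.3.3 give different answers on PR, and 12.2.1.1 admits them to the objective-response set only as early failures.

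The consequence is confined to the descriptive summary for aim 1.2.1. A reader might go further and take this as a threat to the dose conclusion or to a planned test of activity. The documents do not support that: response feeds no decision rule, test or target rate, and DLT, MTD and sample size do not depend on it. Nor do the activity figures in Section 2.1.4 (8 of 50 and 6 of 71) give a benchmark, since they come from other regimens and, in the first case, from neuroblastoma alone.

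The size cannot be fixed from the documents, because it depends on how many MIBG-only patients enroll. In case A the rate runs from 8.3% to 16.7% according to the section used. With no MIBG-only patients, the MIBG part of the problem has no effect.

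**What to change.** 1. In 12.2.1.1, widen the baseline condition to *measurable disease, or MIBG-positive disease assessed under 12.4*. Exclude those MIBG-positive patients from 12.2.1.2, so that nobody sits in both sets.
2. In 12.2.1.1, limit the early-progression clause to patients whose baseline disease would otherwise place them in the objective-response set. Other evaluable-only patients are then no longer counted only as failures.
3. In 12.3.3, add *except MIBG-positive neuroblastoma, which is classified under 12.4*. A pointer under Table 2 in 12.2.5 to Table 5 would make the same exception visible there.
4. Leave 12.3.1 unchanged. Section 4.1.4 takes its definitions from 12.2 and 12.3 only, and Section 4.0 has eligibility read literally. An exception in 12.3.1 would make MIBG-only children neither measurable nor evaluable, and so ineligible.
5. In 11.5, state that response is reported with and without MIBG-only patients, each with its matching denominator.

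After the change, cases A and C both give 2/12 = 16.7% with MIBG-only patients and 1/10 = 10.0% without them.

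The cost is wording in four clauses (12.2.1.1, 12.2.1.2, 12.3.3 and 11.5), an optional table note, and one extra row in a descriptive table. No patients or procedures are added. It is best done before the data are summarized, because the choice of section would otherwise be made with the responses known.

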12.2.2 Disease Parameters

12.2.2.1 Measurable disease: Measurable lesions are defined as those that can be accurately measured in at least one dimension (longest diameter to be recorded) as ≥ 20 mm by chest x-ray, as ≥ 10 mm with CT scan, or ≥ 10 mm with calipers by clinical exam. All tumor measurements must be recorded in millimeters (or decimal fractions of centimeters).

Note: Tumor lesions that are situated in a previously irradiated area must show definitive evidence of progression to be considered evaluable.

12.2.2.2 Malignant lymph nodes: To be considered pathologically enlarged and measurable, a lymph node must be ≥ 15 mm in short axis when assessed by CT scan (CT scan slice thickness no greater than 5 mm). At baseline and in follow-up, only the short axis will be measured and followed.

12.2.2.3 Non-measurable disease: All other lesions (or sites of disease), including small lesions (longest diameter < 10 mm or pathological lymph nodes with ≥ 10 to < 15 mm short axis), are considered non-measurable disease. Bone lesions, leptomeningeal disease, ascites, pleural/pericardial effusions, lymphangitis cutis/pulmonitis, inflammatory breast disease, and abdominal masses (not followed by CT or MRI), are considered as non-measurable.

Note: Cystic lesions that meet the criteria for radiographically defined simple cysts should not be considered as malignant lesions (neither measurable nor non-measurable) since they are, by definition, simple cysts. 'Cystic lesions' thought to represent cystic metastases can be considered as measurable lesions, if they meet the definition of measurability described above. However, if non-cystic lesions are present in the same patient, these are preferred for selection as target lesions.

12.2.2.4 Target lesions: All measurable lesions up to a maximum of 2 lesions per organ and 5 lesions in total, representative of all involved organs, should be identified as target lesions and recorded and measured at baseline. Target lesions should be selected on the basis of their size (lesions with the longest diameter), be representative of all involved organs, but in addition should be those that lend themselves to reproducible repeated measurements. It may be the case that, on occasion, the largest lesion does not lend itself to reproducible measurement in which circumstance the next largest lesion that can be measured reproducibly should be selected. A sum of the diameters (longest for non-nodal lesions, short axis for nodal lesions) for all target lesions will be calculated and reported as the baseline sum diameters. If lymph nodes are to be included in the sum, then only the short axis is added into the sum. The baseline sum diameters will be used as reference to further characterize any objective tumor regression in the measurable dimension of the disease.

12.2.2.5 Non-target lesions: All other lesions (or sites of disease) including any measurable lesions over and above the 5 target lesions should be identified as non-target lesions and should also be recorded at baseline. Measurements of these lesions are not required, but the presence, absence, or in rare cases unequivocal progression of each should be noted throughout follow-up.

12.2.3 Methods for Evaluation of Measurable Disease

All measurements should be taken and recorded in metric notation using a ruler or calipers.

The same method of assessment and the same technique should be used to characterize each identified and reported lesion at baseline and during follow-up. Imaging-based evaluation is preferred to evaluation by clinical examination unless the lesion(s) being followed cannot be imaged but are assessable by clinical exam.

- 12.2.3.1 Clinical lesions: Clinical lesions will only be considered measurable when they are superficial (e.g., skin nodules and palpable lymph nodes) and ≥ 10 mm diameter as assessed using calipers (e.g., skin nodules). In the case of skin lesions, documentation by color photography, including a ruler to estimate the size of the lesion, is recommended.
- 12.2.3.2 Chest x-ray: Lesions on chest x-ray are acceptable as measurable lesions when they are clearly defined and surrounded by aerated lung. However, CT is preferable.
- 12.2.3.3 Conventional CT and MRI: This guideline has defined measurability of lesions on CT scan based on the assumption that CT slice thickness is 5 mm or less. If CT scans have slice thickness greater than 5 mm, the minimum size for a measurable lesion should be twice the slice thickness. MRI is also acceptable in certain situations (e.g. for body scans). Ideally, the same type of scanner should be used and the image acquisition protocol should be followed as closely as possible to prior scans.
- 12.2.3.4 PET-CT: At present, the low dose or attenuation correction CT portion of a combined PET-CT is not always of optimal diagnostic CT quality for use with RECIST measurements. However, if the site can document that the CT performed as part of a PET-CT is of identical diagnostic quality to a diagnostic CT (with IV and oral contrast), then the CT portion of the PET-CT can be used for RECIST measurements and can be used interchangeably with conventional CT in accurately measuring cancer lesions over time. Note, however, that the PET portion of the CT introduces additional data which may bias an investigator if it is not routinely or serially performed.
- 12.2.3.5 Tumor markers: Tumor markers alone cannot be used to assess response. If markers are initially above the upper normal limit, they must normalize for a patient to be considered in complete clinical response.
- 12.2.3.6 Cytology, Histology: These techniques can be used to differentiate between partial responses (PR) and complete responses (CR) in rare cases (e.g., residual lesions in tumor types, such as germ cell tumors, where known residual benign tumors can remain).

Cytology should be obtained if an effusion appears or worsens during treatment when the measurable tumor has met criteria for response or stable disease.

12.2.3.7 FDG-PET: While FDG-PET response assessments need additional study, it is sometimes reasonable to incorporate the use of FDG-PET scanning to complement CT scanning in assessment of progression (particularly possible 'new' disease). New lesions on the basis of FDG-PET imaging can be identified according to the following algorithm:

- a. Negative FDG-PET at baseline, with a positive FDG-PET at follow-up is a sign of PD based on a new lesion.
- b. No FDG-PET at baseline and a positive FDG-PET at follow-up: If the positive FDG-PET at follow-up corresponds to a new site of disease confirmed by CT, this is PD. If the positive FDG-PET at follow-up is not confirmed as a new site of disease on CT, additional follow-up CT scans are needed to determine if there is truly progression occurring at that site (if so, the date of PD will be the date of the initial abnormal FDG-PET scan). If the positive FDG-PET at follow-up corresponds to a pre-existing site of disease on CT that is not progressing on the basis of the anatomic images, this is not PD.

Note: A 'positive' FDG-PET scan lesion means one that is FDG avid with an uptake greater than twice that of the surrounding tissue on the attenuation corrected image.

12.2.4 Response Criteria for Patients with Solid Tumor and Measurable Disease

12.2.4.1 Evaluation of Target Lesions

Complete Response (CR): Disappearance of all target and non-target lesions. Any pathological lymph nodes (whether target or non-target) must have reduction in short axis to <10 mm. If immunocytology is available, no disease must be detected by that methodology. Normalization of urinary catecholamines or other tumor markers if elevated at study enrollment (for patients with neuroblastoma).

Partial Response (PR): At least a 30% decrease in the sum of the diameters of target lesions, taking as reference the baseline sum diameters

Progressive Disease (PD): At least a 20% increase in the sum of the diameters of target lesions, taking as reference the smallest sum on study (this includes the baseline sum if that is the smallest on study). In addition to the relative increase of 20%, the sum must also demonstrate an absolute increase of at least 5 mm. (Note: the appearance of one or more new lesions is also considered progressions). Note: in presence of SD or PR in target disease but unequivocal progression in non-target or non-measurable disease, the patient

has PD if there is an overall level of substantial worsening in non-target disease such that the overall tumor burden has increased sufficiently to merit discontinuation of therapy

Stable Disease (SD):

Neither sufficient shrinkage to qualify for PR nor sufficient increase to qualify for PD, taking as reference the smallest sum diameters while on study

